8 DATA MANAGEMENT

Procedures Description	
SOP CLP688 Processing Paper CRF Received from Investigational Sites describes activities related to data processing and data management. Overall responsibilities as stated in the SOP are as follows:
 
The Sponsor of the clinical investigation is responsible for:
 
 • Maintaining records to document the compliance of all parties involved in the clinical investigation • Ensuring that the clinical investigation is correctly monitored at the investigation site according to the monitoring plan 
The Monitor is responsible for:
 
 • Monitoring the clinical investigation at the investigation site, according to 934CLD Clinical Investigation Monitoring Plan and SOP 633CLP Monitoring Clinical Investigations, ensuring that: 
 ○ CRFs and queries are complete, recorded in a timely manner, and consistent with source documents ○ Appropriate corrections, additions or deletions are made to the CRFs, dated, explained if necessary and initialed by the principal investigator or by his/her authorized designee • Maintaining detailed shipping records for transmission of completed paper CRFs to Sponsor / CRO 
The Principal investigator (PI) for the clinical investigation is responsible for:
 
 • Ensuring the accuracy, completeness, legibility and timeliness of the data reported to the sponsor in the CRFs and in all required reports during the clinical investigation • Supporting the sponsor or CRO and responding to questions during monitoring and close-out of the clinical investigation at the investigation site 
The Site Clinical Coordinator for the clinical investigation is responsible for:
 
 • Maintaining all of the study related hospital files 
 ○ This includes maintaining all logs such as: 
 ▪ Clinical Investigation Plan (CIP) Deviation Log ▪ Subject Informed Consent (SIC) Signature Log ▪ Investigation Team Log ▪ Device Accountability Log ▪ Investigation Site Team Training Log ▪ Clinical Investigation Document Approval Log ▪ CIP Amendment Log • Correct filling of the CRFs based on source documentation and live documentation • Maintaining contact with study subjects, and coordinating visits to the hospital for signing documents and undergoing treatment • Providing the subjects with the bowel cleanse preparation medications (sponsor provided)
-------------------------------	--

Clinical Investigational Plan

Protocol ID	934CLD	Sponsor	GI View Ltd.
Revision	03	Investigational Device	Aer-O-Scope® Colonoscope System

	
 Instructing subjects on proper diet and other study related issues Ensuring 24-48 hour follow-up phone calls are made Maintaining contact with the sponsor for all reportable incidents and general updates 
The Data Manager is responsible for:
 
 Managing CRF receipt and reconciliation of any discrepancies prior to data entry Performing manual review of the CRF to verify completeness and legibility, data content and consistency Ensuring that all SAEs have been reported to the Sponsor Performing CRF data entry into the clinical data base Maintaining the CRF Tracking Form (689CLP), recording data receipt & reconciliation, manual review, data changes, data queries and data entry
Retention Period	All original copies of CRFs and completed forms will be stored in the Trial Master File in accordance with 674CLP Trial Master File Management for a period of no less than five (5) years.
Clinical Quality Assurance	
Study File Monitoring
 
 Prior to study implementation, a monitoring schedule will be set and logged into the 642CLP Monitoring Schedule Form. Tracking of planned and actual visits will also be performed using this form. At the start of the clinical study, the Clinical Monitor will monitor the study files for the following: 
 IRB/EC/Helsinki Committee Documents 
 All IRB Correspondence is on file The study staff are IRB approved prior to performing any study procedures Adverse events and deviation procedures for reporting to IRB per current guidelines are in place All versions of the IRB protocols and informed consent forms are on file FDA 
 Signed Good Clinical Practice compliance form, financial disclosure and CV for the PI and sub investigators All FDA correspondence, if applicable Procedures of documentation of serious adverse events that are unexpected and related for reporting to FDA within 7 calendar days are in place Other documents: 
 CVs for all study staff are on file and updated within the last 2 years Medical licenses for the Sub-Investigators are on file and updated prior to expiration Delegation Log is updated and procedures for updating the log with new staff are in place All other essential documents have been prepared and

Clinical Investigational Plan

Protocol ID	934CLD	Sponsor	GI View Ltd.
Revision	03	Investigational Device	Aer-O-Scope® Colonoscope System

	
completed as appropriate
 
Before, during and at the close of the study period, study documentation will be monitored by the Clinical Monitor for the following:
 
 • Informed Consent • Ensure that subject identification is on all pages of the ICF, if applicable • Documentation of subject receiving a copy of the consent form is present • Clinic note documents informed consent process • The subject and study representative signed and dated the consent form for him/herself • The subject initialed and dated all appropriate pages on the informed consent form, if applicable • Note to file completed for any informed consent deviations. • Ensure a valid (current version date) copy of the consent form was used 
Protocol:
 
 • Confirm that the study staff is conducting the study in compliance with the protocol approved by IRB/CE/Helsinki Committee and if applicable, FDA. • The protocol deviations (exceptions and violations) are documented in the subject chart and reported to IRB/CE/Helsinki Committee as required. • Ensure any deviations are logged in FORM 638CLP CIP Deviations 
Source Documents:
 
 • Review subject charts to ensure accuracy, completeness and legibility of the data • Any correction made to the source documents is dated, initialed, and explained. The original entry should not be obscured. • The protocol specific source documents are on file. • Source documents are completed in ink. • Note to files are generated for missing or incomplete data, and to explain any discrepancies or additional comments. 
Case Report Forms:
 
 • Ensure that the data reported on the CRF is consistent with the source documents. • Discrepancies between the source documents and CRF are explained in a note to file or captured in a comment in the CRF. 
Query Management
 
Queries may be generated by the PI, Sub-investigators, Sponsor, Monitor or Data Center.
 
Query management will be handled by the Clinical Monitor using the 639CLP CRF & Query Monitoring Log.
 
The Clinical Monitor will create a Monitoring Report using the 637CLP

--	---

Clinical Investigational Plan			
Protocol ID	934CLD	Sponsor	GI View Ltd.
Revision	03	Investigational Device	Aer-O-Scope® Colonoscope System

	
Monitoring Report FORM.
 
Samples of data queries are as follows:
 
 • Non-compliance to protocol • Missing data • Out-of-range data • Unplanned patient visits • Data inconsistent with the source documents • Data clarification
--	---

9 AMENDMENTS TO THE CIP

Amendments	
All subsequent amendments to the CIP must also be agreed and approved by the sponsor, the coordinating investigator and all principal investigators.
 
The Sponsor / CRO will ensure that
 
9.1 Amendments to the Clinical Investigation Plan are documented, using form 698CLP 'CIP Amendment and Revision Sheet'
 
9.2 approval is documented, using form 693CLP 'Clinical Investigation Document Approval Log'
 
9.3 the amended CIP is sent to all investigators and the IRB / EC after approval

-------------------	---

10 DEVIATIONS FROM CLINICAL INVESTIGATION PLAN

Deviations	
Neither the Principal Investigator nor any of the sub-investigators are authorized to deviate from the CIP, except as specified in 4.5.4 b of ISO 14155:2011 and 21 CFR 812.150 (a)(4), specifically requests for deviations, and reports of deviations, if the deviation affects subject's rights, safety and wellbeing, or the scientific integrity of the clinical investigation.
 
Under emergency circumstances, deviations from the CIP to protect the rights, safety and well-being of human subjects may proceed without prior approval of the sponsor and the EC/IRB/Helsinki Committee. Such deviations shall be documented and reported to the sponsor and the EC/IRB/Helsinki Committee as soon as possible.

Procedures	
According to 633CLD Monitoring Clinical Investigations, after completion of the monitoring visit, the monitor will prepare the EC/IRB /Helsinki Committee Notifications letter using form 644CLP EC Notification Form if any reportable serious deviations or adverse events were recorded, and send them to the Ethics Committee/Institutional Review Board/Helsinki Committee and Principal Investigator, according to this CIP.

Notifications	
All notifications will be carried out within the time frames specified by local regulatory authorities or as noted in 934CLD Clinical Investigation Monitoring Plan (for this CIP)

Clinical Investigational Plan			
Protocol ID	934CLD	Sponsor	GI View Ltd.
Revision	03	Investigational Device	Aer-O-Scope® Colonoscope System

Other	
Investigational site activities will be monitored prior to, throughout, and following the conduct of the clinical investigation to ensure that all criteria are met as per this Clinical Investigation Plan.
 
In the event that responsibilities are not met by participating personnel, the sponsor reserves the right to disqualify the specific parties involved, specifically the Principal Investigator, as follows:
 
 • Accuracy, completeness, legibility and timeliness of the data reported to the sponsor in the CRFs and in all required reports during the clinical investigation are not carried out or are compromised • Resources are not provided in order to facilitate the operation of the investigational study • Any unethical actions related to the investigation and/or serious deviations from the CIP and/or written procedures 
In the event that monitoring activities reveal any areas of concern, the PI will be notified in writing and corrective actions will be established. Should the event occur repeatedly, the PI/Site may be disqualified.

--------------	---

11 DEVICE ACCOUNTABILITY

procedures for accountability of investigational devices	
690CLP Device Inventory & Accountability describes all procedures for device shipping, accountability, storage, use and return.
 
Responsibilities are as follows:
 
The Sponsor of the clinical investigation is responsible for:
 
 • Maintaining records to document the compliance of all parties involved in the clinical investigation • Keeping records to document the physical location of all investigational devices from shipment of investigational devices to the investigation sites until return or disposal • Monitoring clinical activities at the investigation site according to the monitoring plan, to ensure that investigational device accountability records are accurate and complete 
The Principal investigator (PI) for the clinical investigation is responsible for:
 
 • Keeping records documenting the receipt, use, return and disposal of the investigational devices at the site • Supporting the sponsor or CRO and responding to questions during monitoring and close-out of the clinical investigation at the investigation site
---	---

Clinical Investigational Plan			
Protocol ID	934CLD	Sponsor	GI View Ltd.
Revision	03	Investigational Device	Aer-O-Scope® Colonoscope System

12 STATEMENTS OF COMPLIANCE

- 12.1 This clinical investigation will be conducted in accordance with ethical principles stated in the Declaration of Helsinki and in compliance with all national and local regulatory requirements for the safety and protection of human subjects.
- 12.2 This clinical investigation will be implemented only upon receiving all final notification/authorizations from local and national regulatory and Helsinki/EC/IRB authorities, as appropriate.
- 12.3 This clinical investigation will comply with any additional requirements set forth by the Helsinki/EC/IRB and/or regulatory authorities.
- 12.4 This clinical investigation provides clinical study medical insurance for study participants as required by local and national regulatory authorities.

13 INFORMED CONSENT PROCESS

General process	
Subjects interested in participating in the clinical investigation will be screened by the clinical coordinator or participating physician.
 
Subjects who meet the criteria will then be given a copy of the Patient Informed Consent prior to receiving the medication for the bowel prep, with ample time to read and review the document and ask questions prior to signing.
 
Subjects will meet with one of the investigators or the clinical coordinator to discuss investigational participation and any questions they may have regarding the investigation, the investigational device and the informed consent.
 
The informed consent will be signed during the meeting with one of the participating investigators.
 
A photocopy of the signed patient informed consent form will be provided to the patient prior to the procedure.
 
Subjects requesting to withdraw consent will be disqualified from the investigation at no cost or consequence.

Unable subject	Subjects unable to provide consent on their own behalf will not be recruited into the study.
Emergency treatment	In the event of an emergency resulting from the clinical investigation, all emergency treatment will be provided at no cost to the patient. Clinical Investigation Insurance has been provided to ensure all costs be covered if necessary.

Clinical Investigational Plan			
Protocol ID	934CLD	Sponsor	GI View Ltd.
Revision	03	Investigational Device	Aer-O-Scope® Colonoscope System

14 ADVERSE EVENTS, ADVERSE DEVICE EFFECTS AND DEVICE DEFICIENCIES

Definitions	
An adverse event is any undesirable or unintentional or unexpected event (sign, symptom, illness, abnormal laboratory value, or other medical event) that occurs during the course of the study, whether or not considered related to the device. This definition includes events related to the investigational medical device or the comparator and also includes events related to the procedures involved.
 
Regardless of the relationship to the investigational device, all moderate to serious adverse events occurring from the time that the informed consent is signed must be recorded in the patient's CRF. Mild expected adverse events such as flatulence, nausea, diarrhea, bloating, mild abdominal cramping, anal discomfort, minor rectal bleeding (specifically if therapeutic intervention is performed), headache, dizziness, thirst, tenesmus or any other symptoms not requiring treatment will not be recorded. These events are common and expected. For device operators, this definition is restricted to the events related to the investigational medical device.
 
A mild adverse event is one that the symptoms are barely noticeable to the patient. It does not influence performance, require drug treatment or prevent the patient from carrying on with normal life activities.
 
A moderate adverse event is one that the symptoms make the patient uncomfortable and causes some impairment to normal life activities and requires treatment for symptom(s).
 
A serious adverse event an adverse event that:
 
 • Led to death, • Led to serious deterioration in the health of the subject, that either resulted in 
 ○ A life-threatening illness or injury, or ○ A permanent impairment of a body structure or body function, or ○ In-patient or prolonged hospitalization, or ○ Medical or surgical intervention to prevent life-threatening illness or injury or permanent impairment to a body structure or a body function 
An adverse device effect (ADE) is an event related to the use of an investigational medical device. This includes any adverse event resulting from the insufficiencies or inadequacies in the instructions for use, the deployment, the implantation, the installation, the operation or any malfunction of the investigational medical device. This also includes user error or intentional misuse of the investigational medical device.
 
A device deficiency is an inadequacy of a medical device related to its identity, quality, durability, reliability safety or performance, such as malfunction, misuse or use error and inadequate labeling.
 
An unanticipated serious adverse device effect (USADE) is a serious adverse device effect which by its nature, incidence, severity or outcome has not been identified in the current version of the risk analysis report / Investigator's Brochure.

Principal Investigator	The principal investigator will notify the sponsor immediately (within 24 hours) of any serious adverse event or serious adverse device effect and

Clinical Investigational Plan			
Protocol ID	934CLD	Sponsor	GI View Ltd.
Revision	03	Investigational Device	Aer-O-Scope® Colonoscope System

	within 48 hours for any other adverse device effect. All reports to the appropriate authorities will be made by the principal investigator as set forth in the standard clinical practices outlined in the 21 CFR (§ 812.150(a)(1), § 812.46(b) and § 812.150(b)(1))/ MEDDEV 2.7/3 Dec 2010 and ICH-GCP Guidelines.
Adverse Events Report	Adverse Events will be reported and treated as per the standard clinical practices outlined in the 21 CFR (§ 812.150(a)(1), § 812.46(b) and § 812.150(b)(1))/ MEDDEV 2.7/3 Dec 2010 and ICH-GCP Guidelines.
Device Deficiencies Report	All device deficiencies related to the identity, quality, durability, reliability, safety or performance of the investigational medical device shall be documented throughout the clinical investigation and appropriately managed by the sponsor.
Foreseeable Adverse Events and Anticipated Adverse Device Effects	Anticipated adverse events include minor bloating, stomach ache, flatulence, nausea, vomiting, light headedness, minor mucosal erosions and rectal fissures. Anticipated adverse device effects include problems related to the suction system that may hinder visualization, temporary irrigation problems due to kinks in the tubing resulting from a tortuous colon etc.
Emergency Contact Details	In the event of a serious adverse event and/or a serious adverse device effect, the following sponsor representative should be contacted immediately: [name] VP Regulatory and Clinical [contact]hours a day, 7 days a week) Email: [contact] [contact]
Data Monitoring Committee DMC	An independent data safety monitoring board (DSMB) of at least three (3) gastroenterologists will review any and all adverse events and device deficiencies. Chairing the committee will be [name].

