4 INVESTIGATIONAL DEVICE AND CLINICAL INVESTIGATION RISKS & BENEFITS

Risks	
The risks associated with the Aer-O-Scope Colonoscope are similar to those risks associated with conventional optical colonoscopy. As with all procedures related to colon screening, there are some associated risks. Risks associated with both colonoscopy and the Aer-O-Scope Colonoscope may include but are not limited to the following:
 
 • Lower digestive tract bleeding, • Colon perforation (that may result in inflammation of the peritoneum (peritonitis) or need for emergency medical treatment), • Excessive insufflation of the colon, • Erosion of the colon mucosa, • Sepsis • Venous thrombosis, • Vasovagal events, • Pain, • Ano-rectal Fissures, • Bloating and • Discomfort. 
Anticipated adverse device effects include bloating, flatulence mild in nature, ano-rectal fissures and minor discomfort. These symptoms are all transient and do not pose a potential risk to the subjects’ health.
 
The Aer-O-Scope Colonoscope system has been designed to minimize

--------------	---

Clinical Investigational Plan

Protocol ID	934CLD	Sponsor	GI View Ltd.
Revision	03	Investigational Device	Aer-O-Scope® Colonoscope System

	these adverse effects.

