LIKERT SCALE	USABILITY												
1	Easy to perform												
2	Slightly complicated to perform												
3	Neutral (Neither easy nor difficult)												
4	Complicated to perform												
5	Very Complicated to perform												

Clinical Investigational Plan			
Protocol ID	934CLD	Sponsor	GI View Ltd.
Revision	03	Investigational Device	Aer-O-Scope® Colonoscope System

	conventional colonoscopes will be equivalent.
Claims and Performance	The Aer-O-Scope Colonoscope System will have a lower overall number of missed adenomas as compared with conventional forward-viewing colonoscopy. An interim analysis will be performed upon completion of each study site.
Risks and Adverse Effects	All serious adverse events and unexpected adverse events as well as adverse device effects will be evaluated in the course of this study.

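### The rule that mild events and symptoms not needing treatment are not recorded conflicts, for mild device-related symptoms, with the plan's own rules that adverse device effects be notified, evaluated and reviewed

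*Combined protocol and SAP*

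**What the plan says.** **What is recorded.** Section 14 (Definitions) sets the threshold for the case report form (CRF). Whatever the relationship to the device, "all moderate to serious adverse events occurring from the time that the informed consent is signed must be recorded in the patient's CRF".

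**What is not.** The next sentence begins "Mild expected adverse events such as flatulence, nausea, diarrhea, bloating, mild abdominal cramping, anal discomfort, minor rectal bleeding", continues to "headache, dizziness, thirst, tenesmus or any other symptoms not requiring treatment", and ends with the instruction that these "will not be recorded". The plan explains that such events are common and expected.

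**Severity grades.** Section 14 calls an event mild when the patient barely notices it and it neither needs drug treatment nor limits normal life. It calls an event moderate when it causes discomfort and some impairment and also requires treatment.

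**What must be notified, evaluated and reviewed.** Section 14 defines an ADE as an event related to use of the investigational device and sets no lower limit on severity. The investigator notifies serious events within 24 hours and must also notify "within 48 hours for any other adverse device effect". The DSMB "will review any and all adverse events and device deficiencies". Section 5 (Risks and Adverse Effects) adds: "All serious adverse events and unexpected adverse events as well as adverse device effects will be evaluated in the course of this study".

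**What is anticipated.** Section 4 says: "Anticipated adverse device effects include bloating, flatulence mild in nature, ano-rectal fissures and minor discomfort". Section 14 (Foreseeable Adverse Events and Anticipated Adverse Device Effects) differs. It puts bloating, flatulence and fissures under anticipated adverse events, and gives suction and irrigation problems as the anticipated ADEs.

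**The concern.** One instruction tells sites not to write down a class of events. Three others assume that events in that class are known: to the investigator, who must notify them; to the sponsor, who must evaluate them; and to the DSMB, which must review them. A site that sees mild bloating and judges it related to the Aer-O-Scope has no way to satisfy all four.

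Primary objective 1.2 is to show that the system is safe, and the device advances by balloons and CO₂ rather than as a conventional scope does. Section 4 states that the anticipated effects are transient and carry no risk to health. For their mild form the trial would hold no data to support that statement, and the DSMB would not see a pattern of minor symptoms if one arose. Minor events not noted at the time cannot be reliably recovered later.

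**Working it through.** The plan states no figure on this point, so there is nothing to reproduce. The check sets the rules side by side.

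**Step 1. Do the rules collide?** Take a mild symptom, expected, needing no treatment, and judged related to the Aer-O-Scope.

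| Rule | Where | Result for this event |
|---|---|---|
| CRF threshold | Section 14, Definitions | Not required: below moderate, and relationship does not matter |
| Non-recording instruction | Section 14, Definitions | Must not be recorded |
| ADE definition | Section 14, Definitions | It is an ADE |
| Sponsor notification | Section 14, Principal Investigator | Must be notified within 48 hours |
| Evaluation | Section 5, Risks and Adverse Effects | Must be evaluated |
| DSMB review | Section 14, Data Monitoring Committee | Must be reviewed |

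No section exempts mild ADEs from the last three rules, and none exempts device-related events from non-recording. The collision is explicit.

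**Step 2. Which anticipated effects are caught?**

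| Section 4 anticipated ADE | Under the non-recording rule | If moderate or worse |
|---|---|---|
| Bloating | Named | Recorded |
| Mild flatulence | Named | Mild by its own description |
| Minor discomfort | Anal discomfort is named; the rest falls to the closing phrase | Recorded |
| Ano-rectal fissures | Not named; caught only if mild and needing no treatment | Recorded |

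So 3 of 4 are uncollected in their mild form, and the fourth is in part. The technical ADEs in Section 14's own list are less exposed, because that section requires all device deficiencies to be documented.

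**Step 3. Do the severity grades cover every case?**

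- Barely noticeable, no treatment: mild, and not recorded if expected.
- Uncomfortable, impairing and requiring treatment: moderate, and recorded.
- Uncomfortable or limiting, but not requiring treatment: too much for mild, and lacking the treatment element of moderate.

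The third case has no grade. The CRF threshold does not require it, and the open-ended closing phrase can be read to exclude it. Whether it is recorded then turns on whether treatment was needed rather than on how the patient was affected.

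**Step 4. What does the gap reach?** The primary safety endpoint (Section 1.5, endpoint 1.2) counts serious adverse events and serious ADEs. Both are recorded, so it is untouched. Section 7 plans no analysis of mild-event rates, so no planned test changes. What is lost is the count of mild symptomatic ADEs in the planned 310 subjects, and the DSMB's sight of them.

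**The case against.** Several points on the other side have weight.

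- **The threshold is deliberate.** This is a post-market study that states its cut-off openly and gives a reason. That defends having a cut-off. It does not remove the conflict with the notification and review rules, which have none. The conflict could be cured on paper by exempting mild ADEs from those rules, but the plan does not do this, and the data would still be missing.
- **Section 14's own list makes the anticipated ADEs technical.** On that list, bloating and flatulence are adverse events, and suction or irrigation faults would be documented as deficiencies. But Section 4 calls the same symptoms ADEs, the ADE definition turns on relationship to the device, and the DSMB is to review adverse events of every kind. The mismatch between the lists is part of the fault.
- **Non-recording may mean only the CRF, with notification by another route.** The instruction is not worded that way. Even if it were, Section 8 builds the clinical database from the CRFs, so events notified elsewhere would not reach it by the route described.
- **Attribution is weak in any case.** Each subject has both scopes back to back, after bowel preparation and under sedation, with one call at 24-48 hours. This stands: mild symptoms after the procedures could be tied to one scope only in part.

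A reader might also infer that unexpected symptoms are ordered off the CRF. The documents do not clearly say so. The sentence opens with mild expected events, so its closing phrase can be read as limited to those. On that reading an unexpected mild symptom is not barred, although the CRF threshold does not require it either, and Section 5 says unexpected events will be evaluated.

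**Conclusion.** The point holds as a contradiction within the plan. For mild device-related symptoms, the non-recording instruction in Section 14 cannot be followed together with 48-hour notification and DSMB review in the same section and evaluation in Section 5. It catches three of Section 4's four anticipated ADEs in their mild form, and the severity definitions leave a class of untreated but bothersome symptoms without a grade. This rests on the wording alone and on no assumed rate.

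Three stronger readings are not supported:

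- **That anticipated device effects would show a frequency of zero.** Moderate and serious forms are recorded, and the mild forms are uncollected rather than observed as absent.
- **That the primary safety result is compromised.** Its endpoint is serious events only.
- **That full recording would yield a rate for the Aer-O-Scope of known precision.** The documents give no ADE rates, so any precision figure would rest on an assumed one, and it would largely describe the tandem session rather than one device.

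This should be corrected because it affects the wider safety profile and the basis of DSMB review. It does not threaten the primary analysis.

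**What to change.** 1. Reconcile Sections 4, 5 and 14 to one recording rule and one list of anticipated ADEs, saying which are symptoms and which are technical faults.
2. Narrow the exemption so that it does not cover events judged possibly related to the Aer-O-Scope, unexpected symptoms, or symptoms that are more than barely noticeable. Expected, barely noticeable symptoms judged unrelated to the device can stay exempt.
3. Amend the severity definitions so that a symptom that is uncomfortable or limiting but needs no treatment has a grade.
4. Capture the events brought back in by step 2 on a short CRF checklist, completed at the procedures and at the 24-48 hour telephone call already planned. Record severity, relationship, and the pass in which the symptom arose where that is known.
5. State that notification, evaluation and DSMB review draw on the same record.

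The cost is one checklist, slightly longer calls, and more minor events to enter and tabulate. No extra visit or subject is needed, and the primary endpoints do not change.

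### Section 14's severity classes leave some non-serious adverse events with no class and no recording duty, and sections 4 and 14 disagree on which events are anticipated device effects

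*Combined protocol and SAP*

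**What the plan says.** **Recording.** Section 14 (Definitions) sets the duty: "all moderate to serious adverse events occurring from the time that the informed consent is signed must be recorded in the" CRF, whatever their relation to the device. It then states what is left out: "Mild expected adverse events such as flatulence, nausea, diarrhea, bloating, mild abdominal cramping, anal discomfort, minor rectal bleeding", followed by further symptoms and ending with "tenesmus or any other symptoms not requiring treatment". The reason given is that these are common and expected.

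**Severity.** In the same row, mild means barely noticeable, with no effect on performance, no need for drugs and no bar to everyday activity. Moderate means that the symptoms make the patient uncomfortable, and the event also "causes some impairment to normal life activities and requires treatment for symptom(s". An adverse device effect is any event related to use of the device, with no severity threshold.

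**Notice and review.** The principal investigator tells the sponsor of serious events within 24 hours and "within 48 hours for any other adverse device effect". Section 5 (Risks and Adverse Effects) adds: "All serious adverse events and unexpected adverse events as well as adverse device effects will be evaluated in the course of this study". The safety board "will review any and all adverse events and device deficiencies".

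**Anticipated effects.** Section 4 (Risks) says: "Anticipated adverse device effects include bloating, flatulence mild in nature, ano-rectal fissures and minor discomfort". Section 14 (Foreseeable Adverse Events and Anticipated Adverse Device Effects) puts minor bloating, flatulence and rectal fissures under adverse events. As anticipated device effects it gives suction and irrigation problems.

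**The concern.** Demonstrating safety is primary objective 1.2. The severity classes decide which non-serious events must reach the CRF, and section 8 describes CRF data entry as the route into the clinical database. If the classes do not cover every event, two sites can treat the same event differently and both comply. The exposed case matters clinically: abdominal pain that keeps a subject from normal activity for a day but is never treated.

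The two lists of anticipated device effects create a second inconsistency. Whether post-procedure bloating or a fissure triggers the 48-hour notice depends on the section that a site consults. Counts of device effects across the three sites could then partly reflect which list was used.

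**Working it through.** The protocol states no figure on this point, so the check sets its rules side by side.

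**Step 1: severity against the recording duty.** Each non-serious event is classified by whether it impairs activity and whether it is treated.

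| Impairs activity | Treated | Class under section 14 | CRF entry required |
|---|---|---|---|
| No | No | Mild, if barely noticeable | No; excluded if expected |
| Yes | Yes | Moderate, if uncomfortable | Yes |
| Yes | No | None | No |
| No | Yes (drug) | None | No |

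One cell of four carries a duty. The third row fails mild because activity is affected, and fails moderate because there is no treatment. The fourth fails mild because a drug was needed, and fails moderate because nothing was impaired.

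**Step 2: the closing words of the exclusion.** If they extend the list of mild expected events, the third row is not barred from the CRF but is still not required. If they stand alone, the third row is barred. The sentence allows both readings. The fourth row is outside these words either way, since it was treated.

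**Step 3: the lists of device effects.**

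| Event | Section 4 | Section 14, foreseeable events | Section 14, not recorded |
|---|---|---|---|
| Bloating | Device effect | Adverse event | Named |
| Flatulence | Device effect (mild) | Adverse event | Named |
| Ano-rectal fissures | Device effect | Adverse event (rectal fissures) | Not named |
| Minor discomfort | Device effect | Not named as such | Anal discomfort named |
| Suction and irrigation problems | Not named | Device effect | Not named |

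A site using section 4 notifies mild device-related bloating within 48 hours and leaves it out of the CRF. A site using the section 14 list may do neither.

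**Step 4: size.** The documents give no rate for events in the two unclassified cells. Section 6.3 plans 310 subjects. If 5%, 10% or 20% had such an event, that would be 310 × 0.05 = 15.5, 310 × 0.10 = 31 or 310 × 0.20 = 62 subjects. These rates are assumptions, and the counts are upper bounds on what is missed, because sites may record an event without being obliged to.

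**The case against.** Much can be said for the plan.

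- **The board's remit.** A reader might infer that the board cannot do what section 14 asks of it. The text does not support that: a board reviews what is recorded or notified, and the phrase reads naturally in that sense.
- **Notice against recording.** A reader might infer that a site cannot leave an effect out of the CRF and also notify it. It can: CRF entry and notice to the sponsor are separate channels.
- **Loss of the non-serious profile.** A reader might infer that non-serious safety data are lost altogether. They are not. Non-serious events that are uncomfortable, impairing and treated must be recorded, and device deficiencies must be documented.
- **Mild symptoms.** Leaving out mild expected symptoms is a deliberate choice with a stated reason. Both scopes are used in one session, so a symptom reported at the 24–48 hour call usually could not be assigned to either scope. Counts of mild symptoms would mostly describe the tandem procedure.
- **Other routes.** Section 14 (Adverse Events Report) says that adverse events will be reported under named external standards, section 5 covers unexpected events, and the 48-hour notice catches device-related ones. The CRF (973CLD) and the monitoring plan (935CLD) are separate documents that were not available and may narrow the gap. Both lists of device effects are worded as open, and the general definition could settle a doubtful case.

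These points stand and limit the finding. They do not supply the missing class or a CRF duty for the two unclassified cells, and they do not reconcile the two lists.

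**Conclusion.** The severity classes and the recording rule are wrong as written. Of the four non-serious combinations of impairment and treatment, two have no class and no CRF duty, and the untreated one can be read as barred. The lists in sections 4 and 14 conflict on bloating, flatulence and fissures, so the 48-hour notice may be applied unevenly.

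A reader might infer that the primary safety result is compromised. It is not: primary endpoint 1.2 concerns serious adverse events and serious adverse device effects, which must be recorded and notified within 24 hours. What is at risk is the completeness of the non-serious safety record that supports objective 1.2. The number of events affected is unknown. The conclusion rests on the wording of sections 4, 5 and 14, and assumes that the unseen CRF and monitoring plan do not already correct it. This is a modest point that costs little to put right.

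**What to change.** 1. Define moderate as discomfort with some impairment of normal activity or a need for treatment, so that both unclassified cells must be recorded. Let mild cover the remaining non-serious events; the barely noticeable test would otherwise leave out symptoms that are felt but neither impair activity nor need treatment.
2. Limit the non-recording rule to events that meet the mild definition, by ending its list with *or any other mild expected symptoms*.
3. Use one list of anticipated adverse device effects in sections 4 and 14, and limit the 48-hour notice to non-serious device effects that are moderate or unanticipated.

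The cost is wording changes in sections 4 and 14 and a few more CRF entries. No visits or subjects are added, and mild anticipated effects would no longer trigger the 48-hour notice. A short symptom checklist at the existing 24–48 hour call is optional; its value is limited by the attribution problem noted above.
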